# 8. RESEARCH QUESTION AND OBJECTIVES

Research question:

Is prior receipt of PCV13 associated with reduced risk of major adverse cardiovascular events (MACE) outcomes in adults aged  $\geq 65$  years?

The primary objective of this study is to:

1. Evaluate the effect of PCV13 receipt on the risk of major adverse cardiovascular events (MACE) at 1 and 3 years of follow-up among adults aged ≥65 years

The secondary objectives of this study are to:

PFIZER CONFIDENTIAL CT24-WI-GL02-RF02 6.0 Non-Interventional Study Protocol Template For Secondary Data Collection Study Page 15 of 53

- 1. Evaluate the effect of PCV13 receipt on the risk of myocardial infarction at 1 and 3 years of follow-up among adults aged ≥65 years
- 2. Evaluate the effect of PCV13 receipt on the risk of stroke at 1 and 3 years of follow-up among adults aged ≥65 years
- 3. Evaluate the effect of PCV13 receipt on the risk of hospitalization due to heart failure at 1 and 3 years of follow-up among adults aged ≥65 years
- 4. Examine the degree to which CAP mediates the relationship between PCV13 receipt and MACE at 1 year of follow-up among adults aged >=65 years

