# 9.2.2. Exclusion Criteria

Patients meeting any of the following criteria as of the index date will not have the respective time segment included in the study:

- 1. Evidence of PCV13 vaccination prior to the index date
- 2. Evidence of PPSV23 vaccination in the 365 days prior to the index datea
- 3.  $\geq 1$  diagnosis code for a high-risk condition in the 365 days prior to the index datea
- 4. Evidence of iatrogenic immunosuppression in the 6 months prior to the index date
- 5. Pneumonia diagnosis code in the hospital setting in the 365 days prior to the index datea
- 6. MACE diagnosis code in the hospital, SNF, or LTCF setting in the 365 days prior to the index datea
- 7. Medicare Part C enrollment between September 14, 2014 and the index date
- 8. PCV13 vaccinated individuals with a pneumonia diagnosis code in the hospital setting or a MACE diagnosis code in the hospital, SNF, or LTCF setting in the 13 days after first PCV13 vaccination

a. For adults with  $\geq 6$  months, but less than 365 days of prior continuous enrollment, the exclusion criteria will be evaluated during the continuous enrollment period that the adult has available.

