# 9.3.2. Outcomes

# Table 2.Outcome Variables

Variable	Role	Operational definition	Measurement period
Any MACE	Outcome	
 
≥1 International Classification of Diseases, Ninth Revision, Clinical Modification (ICD-9-CM) or International Classification of Diseases, 10th revision, Clinical Modification (ICD-10-CM) diagnosis code for myocardial infarction, stroke, or heart failure in the hospital, SNF, or LTCF setting.
 
Analyses include first event only and the code must occur one of the following time periods:
 
1. ≥0 days after the unvaccinated index date and before the minimum date of censoring for the unvaccinated time segment
 
2. ≥14 days after the vaccinated index date and before the minim date of censoring for the vaccinated time segment.
 
	Follow-up

PFIZER CONFIDENTIAL

CT24-WI-GL02-RF02 6.0 Non-Interventional Study Protocol Template For Secondary Data Collection Study Page 21 of 53

		ICD-9-CM or ICD-10-CM codes are listed in Appendix Table 2.	
Myocardial infarction	Outcome	≥1 ICD-9-CM or ICD-10-CM diagnosis code for myocardial infarction in the hospital, SNF, or LTCF setting.	Follow-up
		Analyses include first event only and the code must occur one of the following time periods:	
		
 
≥0 days after the unvaccinated index date and before the minimum date of censoring for the unvaccinated time segment
 
	
		
 
≥14 days after the vaccinated index date and before the minim date of censoring for the vaccinated time segment.
 
	
		ICD-9-CM or ICD-10-CM codes are listed in Appendix Table 2.	
Stroke	Outcome	≥1 ICD-9-CM or ICD-10-CM diagnosis code for ischemic stroke in the hospital, SNF, or LTCF setting.	Follow-up
		Analyses include first event only and the code must occur one of the following time periods:	
		
 
≥0 days after the unvaccinated index date and before the minimum date of censoring for the unvaccinated time segment
 
	
		
 
≥14 days after the vaccinated index date and before the minim date of censoring for the vaccinated time segment.
 
	
		ICD-9-CM or ICD-10-CM codes are listed in Appendix Table 2.	
Stroke sensitivity	Outcome	≥1 ICD-9-CM or ICD-10-CM diagnosis code for ischemic or hemorrhagic stroke in the hospital, SNF, or LTCF setting.	Follow-up

CT24-WI-GL02-RF02 6.0 Non-Interventional Study Protocol Template For Secondary Data Collection Study Page 22 of 53

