		
 
Analyses include first event only and the code must occur one of the following time periods:
 
1. ≥0 days after the unvaccinated index date and before the minimum date of censoring for the unvaccinated time segment
 
2. ≥14 days after the vaccinated index date and before the minimum date of censoring for the vaccinated time segment.
 
ICD-9-CM or ICD-10-CM codes are listed in Appendix Table 2.
 
	
Heart failure	Outcome	
 
≥1 ICD-9-CM or ICD-10-CM diagnosis code for heart failure in the SNF, or LTCF setting.
 
Analyses include first event only and the code must occur one of the following time periods: 
 
≥0 days after the unvaccinated index date and before the minimum date of censoring for the unvaccinated time segment
 
≥14 days after the vaccinated index date and before the minimum date of censoring for the vaccinated time segment.
 
 
 
ICD-9-CM or ICD-10-CM codes are listed in Appendix Table 2.
 
	Follow-up
Cataract surgery	Negative control outcome	≥1 International Classification of Diseases, Ninth Revision, Procedure Coding System (ICD-9-PCS), International Classification of Diseases, Tenth Revision, Procedure Coding System (ICD-10-PCS), CPT, or Healthcare Common Procedure Coding System (HCPCS) code for cataract surgery in any setting.	Follow-up

CT24-WI-GL02-RF02 6.0 Non-Interventional Study Protocol Template For Secondary Data Collection Study Page 23 of 53

		
 
Analyses include first event only and the code must occur one of the following time periods:
 
1. ≥0 days after the unvaccinated index date and before the minimum date of censoring for the unvaccinated time segment
 
2. ≥14 days after the vaccinated index date and before the minimum date of censoring for the vaccinated time segment.
 
	
Lipoma	Negative control outcome	
 
≥1 ICD-9-CM or ICD-10-CM diagnosis code for lipoma in any setting.
 
Analyses include first event only and the code must occur one of the following time periods: 
 
≥0 days after the unvaccinated index date and before the minimum date of censoring for the unvaccinated time segment
 
≥14 days after the vaccinated index date and before the minimum date of censoring for the vaccinated time segment.
 
 
 
	Follow-up

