### **Primary Outcome Analysis**

The weighted cumulative incidence function (CIF) will be estimated to describe and account for mortality as a competing risk of MACE. This approach provides a non-parametric estimate of the cumulative incidence function, accounting for the competing risk events. The crude weighted CIF will be presented with the log-rank test to compare the CIF curve between the PCV13 vaccinated and PCV13 unvaccinated cohorts.

A cause-specific Cox proportional hazards model with a time-varying covariate for influenza vaccination status and a time-segment approach to PCV13 vaccination status will be used for the primary analysis. The cause-specific cox model will be used to estimate hazard ratios (HRs) for the first event of each MACE outcome, comparing PCV13 vaccinated with PCV13 unvaccinated Medicare beneficiaries. The model accounts for the possibility of competing risks by focusing on the cause-specific hazard. A time segment approach will be used to account for changes in PCV13 exposure status during follow-up, allowing adults who receive PCV13 during the study period to contribute a PCV13 unvaccinated and a PCV13 vaccinated time segment to the study.

For the any MACE outcome model, individuals are censored after experiencing their first MACE event during a given time segment, irrespective of whether the MACE event is myocardial infarction, stroke, or heart failure. The remaining models examine each type of MACE separately and experiencing one type of MACE event (i.e., myocardial infarction) is not a censoring criterion for the other types of MACE outcomes (i.e., stroke or heart failure) during a given time segment.

The HR for PCV13, with a 95% confidence interval, will be calculated over the follow-up period. If the proportional hazards assumption is violated—indicating the effect of PCV13 on the risk of MACE events changes over time—HRs will be estimated for specific follow-up periods (i.e., 0-1 years and 0-3 years).

[figure not shown]

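### The Table 2 heart failure outcome leaves out the hospital, so secondary objective 3 (heart failure hospitalization) would not be measured

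*Protocol*

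**What the plan says.** Section 8 sets secondary objective 3 as: "Evaluate the effect of PCV13 receipt on the risk of hospitalization due to heart failure at 1 and 3 years of follow-up". The title page table and the abstract state the same objective.

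Table 2 in Section 9.3.2 defines the outcomes. The heart failure row requires at least one "diagnosis code for heart failure in the SNF, or LTCF setting". The related rows are wider:

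- Any MACE: "diagnosis code for myocardial infarction, stroke, or heart failure in the hospital, SNF, or LTCF setting".
- Myocardial infarction: "diagnosis code for myocardial infarction in the hospital, SNF, or LTCF setting".
- Stroke: "diagnosis code for ischemic stroke in the hospital, SNF, or LTCF setting". The stroke sensitivity row uses the same three settings.

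Exclusion 6 in Section 9.2.2 removes time segments with a "MACE diagnosis code in the hospital, SNF, or LTCF setting in the 365 days prior to the index date". Exclusion 8, the 13-day rule after vaccination, applies the same three settings to MACE.

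Section 9.7, Primary Outcome Analysis, says of the component outcomes: "The remaining models examine each type of MACE separately". Heart failure therefore has its own model, and its own Table 2 row decides what that model counts.

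**The concern.** The outcome for a hospitalization objective does not count hospital codes. Read literally, it is a nursing or long-term care endpoint.

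Three things follow:

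- **Events are missed.** Admissions that end in discharge home or in death in hospital are not counted. Admissions followed by facility care are dated from the facility claim, not from the admission.
- **The events that remain are selected.** Whether an admission is counted depends on later use of facility care, which marks frailty. The protocol is already concerned about healthy-vaccinee behavior (Section 9.7, Negative Control Outcomes), so an endpoint tied to frailty is a poor one on which to compare vaccinated and unvaccinated people.
- **The composite and its component disagree.** The heart failure events inside any MACE would not be the events in the heart failure model, so the component result could not be used to explain the composite.

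Independent double programming (Section 9.8) is designed to find differences between two programmers. If both work from the same row, they agree on the same wrong endpoint.

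**Working it through.** **1. Settings side by side (all from the protocol)**

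| Place | Hospital | SNF | LTCF |
|---|---|---|---|
| Objective 3, Section 8 | yes (the only setting named) | not named | not named |
| Any MACE, Table 2 | yes | yes | yes |
| Myocardial infarction, Table 2 | yes | yes | yes |
| Stroke and stroke sensitivity, Table 2 | yes | yes | yes |
| Exclusions 6 and 8, Section 9.2.2 | yes | yes | yes |
| **Heart failure, Table 2** | **no** | yes | yes |

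The heart failure row is the only exception, and it omits the one setting that its objective names.

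**2. Is it repaired elsewhere?** Appendix Table 2 lists diagnosis codes without settings. The baseline heart failure covariate in Table 5 is limited to outpatient codes, which fits the idea that hospital heart failure counts as MACE but does not change the outcome row. No other section defines the separate heart failure outcome.

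**3. One person traced through the rules.** Someone is admitted with heart failure during follow-up, is discharged home and has no facility claim.

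- Any MACE model: event on the hospital code.
- Heart failure model: no event. Follow-up continues until another stopping rule applies.

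The same admission is an event in the composite and a non-event in the component.

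**4. Size.** The documents do not give the share *p* of heart failure admissions that are followed by a heart failure code on a SNF or LTCF claim. Take *p* = 0.20 to 0.40 as an assumption. The share of admissions not counted is 1 − *p*:

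- *p* = 0.20: 1 − 0.20 = 0.80, so 80% are missed.
- *p* = 0.40: 1 − 0.40 = 0.60, so 60% are missed.

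This is the share of *admissions* missed. Facility codes with no preceding admission would be counted, on the same date, under the present row or a corrected one, so the loss as a share of all events in a corrected row would be smaller.

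**5. Effect on the hazard ratio.** For uncommon events, and setting aside facility codes without an admission, the ratio observed is roughly

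observed ratio ≈ true ratio × (*p* in vaccinated ÷ *p* in unvaccinated).

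If *p* is the same in both groups, the ratio is roughly preserved and only events are lost. If the groups differ in how often they enter facility care after an admission, that difference goes straight into the estimate. The documents give no value of *p* by group, so neither the direction nor the size of the bias can be stated.

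**6. Is any stated figure affected?** The protocol gives no event rate, power or sample size for heart failure. The sample sizes in Table 6 concern first any MACE and reproduce. For HR 0.85, control hazard 0.0507, 1 year, 2:3 allocation (k = 2/3), two-sided 5% and 80% power:

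- Freedman events = (1.960 + 0.8416)² × (1 + k × 0.85)² ÷ [k × (1 − 0.85)²] = 7.849 × 2.4544 ÷ 0.0150 ≈ 1,284.
- Average event probability = 0.4 × (1 − e^(−0.0507 × 0.85)) + 0.6 × (1 − e^(−0.0507)) = 0.4 × 0.04218 + 0.6 × 0.04944 = 0.04653.
- Total N = 1,284.3 ÷ 0.04653 ≈ 27,600, against the stated 27,520. The Lakatos method gives 27,571.

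The any MACE row includes the hospital, so these figures do not depend on the heart failure row.

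**The case against.** The best defense is that this is a lost word and not a decision. The comma left in the heart failure row looks like the remains of a three-item list, every parallel row has all three settings, and objective 3 names hospitalization, so a careful programmer would see the intent. That is probably how it arose. It is a reason for an easy correction, not for leaving the row alone, because the written definition is the specification.

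The scope is narrow, and this stands in full. The primary any MACE outcome counts hospital heart failure codes. The myocardial infarction and stroke outcomes, the mediation analysis and the sample size are untouched. Only secondary objective 3, and any Fine-Gray analysis of it, is affected.

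It is also fair to say that programming follows the SAP as well as the protocol and that a final review is planned (Section 9.8), so nobody can be certain that the slip would survive. But Section 9.7 ties a protocol amendment to major changes to primary endpoints. A quiet correction in the SAP could therefore leave the protocol misdescribing this outcome.

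The 60% to 80% loss is only the complement of an assumed share, and not every facility code follows an admission. Both points are right. The contradiction itself depends on neither.

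Finally, adding the hospital does not by itself make the row match objective 3. Facility codes would still count, and the row sets no condition that heart failure be the reason for admission. That also stands and is taken up in the fix.

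**Conclusion.** The concern holds. As written, the heart failure row does not measure the objective it serves, and it contradicts the heart failure part of the primary composite. This rests on the protocol's text alone and needs no outside figure.

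If 20% to 40% of heart failure admissions are followed by a coded SNF or LTCF claim, 60% to 80% of admissions would go uncounted. That range is illustrative. With about 25 million people estimated as eligible, lost precision is not the main issue. What matters is that the endpoint would mean something different and would depend on facility use. The consequence is confined to secondary objective 3, but for that objective it is decisive, so the row should be corrected before programming.

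**What to change.** 1. In Table 2, add the hospital to the heart failure row so that it lists the same three settings as the any MACE, myocardial infarction and stroke rows.
2. Align objective 3 with the row. Either word the objective to cover heart failure coded in hospital, SNF or LTCF, or keep it as hospitalization and restrict the separate heart failure outcome to hospital codes, stating that it is then narrower than the any MACE component.
3. Confirm that the heart failure part of exclusions 6 and 8 is programmed with the three settings already written there, not taken from the present heart failure row.
4. Carry the same definition into the SAP and the program specification.

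The cost is one table cell, the matching program line and, if chosen, one line of objective wording. No new data are needed, and the sample size does not change.

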# 9.3.3. Mediation

### Table 3.Mediation Variables

Variable	Role	Operational definition	Measurement period
Community-acquired pneumonia (CAP)	Mediator	
 
≥1 ICD-9-CM or ICD-10-CM diagnosis code for CAP in any setting, where there were no hospital admissions or ventilator use within the 30 days prior.
 
CAP with be categorized as having 0 or ≥1 CAP event. Individuals will be classified as having ≥1 CAP event if there is at least one diagnosis code for CAP during one of the following time segments:
 
1. ≥0 days after the unvaccinated index date and before the minimum date of censoring for the unvaccinated time segment
 
2. ≥14 days after the vaccinated index date and before the minimum date of censoring for the vaccinated time segment.
 
ICD-9-CM and ICD-10-CM codes are listed in Annex 1.
 
	Follow-up
Community-acquired pneumonia (CAP) sensitivity	Mediator	
 
≥1 ICD-9-CM or ICD-10-CM diagnosis code for CAP in the hospital setting, where there were no hospitalizations or ventilator use in the 30 days prior the hospital admission associated with the CAP diagnosis.
 
For individuals with multiple CAP diagnosis codes during the 1-year follow-up period, CAP will be classified as the highest level of care associated with a CAP diagnosis code.
 
CAP with be categorized as having 0 or ≥1 CAP event. Individuals will be classified as having ≥1 CAP event if there is at least one diagnosis code for
 
	Follow-up

PFIZER CONFIDENTIAL

CT24-WI-GL02-RF02 6.0 Non-Interventional Study Protocol Template For Secondary Data Collection Study Page 25 of 53

CAP during one of the following time segments:

 
≥0 days after the unvaccinated index date and before the minimum date of censoring for the unvaccinated time segment
 

 
4. ≥14 days after the vaccinated index date and before the minimum date of censoring for the vaccinated time segment.
 

ICD-9-CM and ICD-10-CM codes are listed in Annex 1.

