### 9. RESEARCH METHODS

#### 9.1. Study Design

This structured secondary data collection study will be a retrospective cohort study using Centers for Medicare and Medicaid Services (CMS) Medicare data to examine the effect of PCV13 receipt on the risk of MACE among adults aged  $\geq 65$  years in the United States. Individuals will be identified using Medicare Fee-for-Service (FFS) Parts A and B enrollment and claims data.

The analysis will be conducted at the time-segment level using a target trial emulation approach. In this time-segment design, individuals who receive a PCV13 vaccine during the study period can contribute up to two time segments during the follow-up period: a PCV13 unvaccinated time segment and a PCV13 vaccinated time segment. Each segment will be attributed to the appropriate vaccination exposure status cohort, resulting in the individual having two separate index dates included in the analysis. Inclusion/exclusion criteria and baseline characteristics will be assessed separately for these two index dates. For PCV13 unvaccinated patients, multiple eligible times may be identified within the study period, but only the first eligible time will be selected due to the large sample size of the unvaccinated cohort. Individuals who remain unvaccinated throughout the entire follow-up period can contribute a maximum of 1 time segment, which will be attributed to the unvaccinated cohort. All analyses will be conducted based on time-segment level data, which allows the exposure variable – PCV13 vaccination – to be treated as time-invariant within each segment.

The index date for the vaccinated cohort is defined as the date of first PCV13 vaccination. For the unvaccinated cohort, the index date is defined as the date of the first available healthcare claim that occurs after the eligibility date (September 14, 2014) and ensures a six-month period of continuous enrollment prior to the index date. Eligible vaccinated and unvaccinated index dates are 1) between September 14, 2014 and November 30, 2019 and 2) after the individual has at least 6 months of continuous enrollment in Medicare FFS Parts A and B. The 6 months of continuous enrollment prior to the index date for each time segment will be used as the baseline period. Baseline covariates, including demographics, preventative care behaviors, and comorbidities will be assessed during this period.

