Outpatient pneumonia	Patient characteristics	≥1 ICD-9-CM or ICD-10-CM code for pneumonia in the outpatient setting in the 365 days prior to index.	Baseline
Telehealth visits	Patient characteristics	
 
Count of unique days with telehealth visit in the 365 days prior to index.
 
Dichotomous, yes/no
 
Number categories: 0, 1, 2+
 
Continuous statistics including mean, standard deviation (SD), median (Q1 Q3), minimum, and maximum
 
	Baseline
Flu test in the prior 365 days		Influenza test ordered in the 365 days prior to index. • Dichotomous, yes/no	Baseline
Number of labs ordered in the prior 365 days	Patient characteristics	
 
Count of unique days with any lab ordered in the 365 days prior to index
 
Dichotomous, yes/no
 
Number categories: 0, 1, 2+
 
	Baseline

CT24-WI-GL02-RF02 6.0 Non-Interventional Study Protocol Template For Secondary Data Collection Study Page 32 of 53

		• Continuous statistics including mean, standard deviation (SD), median (Q1 Q3), minimum, and maximum	
Number of lipid lab tests ordered in the prior 365 days	Patient characteristics	
 
Count of unique days with a lipid lab ordered in the 365 days prior to index
 
Dichotomous, yes/no
 
Number categories: 0, 1, 2+
 
Continuous statistics including mean, standard deviation (SD), median (Q1 Q3), minimum, and maximum
 
	Baseline
Echocardiogram	Patient characteristics	
 
Count of unique days with an echocardiogram procedure code in the 365 days prior to index.
 
Dichotomous, yes/no
 
Number categories: 0, 1, 2+
 
Continuous statistics including mean, standard deviation (SD), median (Q1 Q3), minimum, and maximum
 
	Baseline
Electrocardiogram	Patient characteristics	
 
Count of unique days with an electrocardiogram procedure code in the 365 days prior to index.
 
Dichotomous, yes/no
 
Number categories: 0, 1, 2+
 
Continuous statistics including mean, standard deviation (SD), median (Q1 Q3), minimum, and maximum
 
	Baseline

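### The main CAP mediator has no new-episode rule, so outpatient pneumonia that began before index, or before day 14 after PCV13, can be counted as follow-up CAP

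*Protocol*

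**What the plan says.** **Mediator (Section 9.3.3, Table 3, main CAP row).** CAP is scored 0 or ≥1 on a single "diagnosis code for CAP in any setting, where there were no hospital admissions or ventilator use within the 30 days prior". Counting runs "≥0 days after the unvaccinated index date and before the minimum date of censoring for the unvaccinated time segment" for unvaccinated segments and "≥14 days after the vaccinated index date and before the minimum date of censoring for the vaccinated time segment" for vaccinated segments.

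**Exclusions (Section 9.2.2).** Exclusion 5 is "Pneumonia diagnosis code in the hospital setting in the 365 days prior to the index date". For the 13-day period following the first dose, exclusion 8 removes "PCV13 vaccinated individuals with a pneumonia diagnosis code in the hospital setting or a MACE diagnosis code in the hospital, SNF, or LTCF setting". As regards pneumonia, both are confined to the hospital.

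**Covariate (Section 9.3.5, Table 5).** Outpatient pneumonia is a baseline characteristic, defined as a "code for pneumonia in the outpatient setting in the 365 days prior to index". People with it stay in the cohort.

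**Unvaccinated index (Section 9.1).** Here "the index date is defined as the date of the first available healthcare claim that occurs after the eligibility date", with no restriction on the type of claim.

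**Sensitivity analysis (Section 9.7).** The mediation analysis is repeated with CAP limited to hospital codes. A separate analysis of non-hospital CAP is mentioned as optional.

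**The concern.** The mediator is measured in a wider set of settings than the exclusions meant to clear earlier pneumonia, and nothing in the CAP row separates a new episode from a follow-up visit for an old one. The 30-day condition concerns hospital admission and ventilator use. It distinguishes community from hospital acquisition, not new from continuing disease.

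The protocol's own reasons for exclusions 5 and 8 (Section 9.2) are that pneumonia is the hypothesized mediator, so its baseline risk should be equalized, and that the vaccine is not taken to be fully effective before day 14. Both reasons apply equally to outpatient episodes once the mediator counts them.

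Pneumonia that began before vaccination, or before assumed protection, cannot transmit a PCV13 effect to MACE. Counting it affects both parts of the product method: the logistic model of CAP on PCV13, and the Cox model in which CAP predicts MACE. It also makes the any-setting and hospital-only results harder to compare, because severity and carry-over are then mixed.

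**Working it through.** **1. Is there a figure in the plan to reproduce?** Not for CAP or mediation. The sample sizes in Section 9.5 concern the MACE log-rank test. They reproduce closely (Freedman form, HR 0.85, 1 year: 27,600 against the stated 27,520) and do not bear on this point.

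**2. The definitions side by side.**

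| Situation | Excluded? | Can a later code score CAP? |
|---|---|---|
| Hospital pneumonia, 365 days before index | Yes (exclusion 5) | Not applicable |
| Outpatient pneumonia shortly before index | No (Table 5 covariate) | Yes, if a further code falls in the window |
| Hospital pneumonia, 13 days after PCV13 | Yes (exclusion 8) | Not applicable |
| Outpatient pneumonia, days 0-13 after PCV13 | No, and onset after index is not covered by the covariate | Yes, if a further code falls on or after day 14 |

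**3. How much carry-over?** The documents give no rates, so every input here is an assumption:
- outpatient pneumonia rate λ: 0.02 to 0.04 a year
- fraction of episodes with a later repeat code f: 0.3 to 0.5
- last repeat uniform over 7-60 days (mean 33.5) or 7-90 days (mean 48.5) after the first code
- true 1-year any-setting CAP risk: 4% to 5%

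Carry-over per segment = λ × f × mean gap / 365.
- Low: 0.02 × 0.3 × 33.5 / 365 = 0.00055, or 5.5 per 10,000. Share of counted CAP: 0.00055 / (0.05 + 0.00055) = 1.1%.
- High: 0.04 × 0.5 × 48.5 / 365 = 0.00266, or 26.6 per 10,000. Share: 0.00266 / (0.04 + 0.00266) = 6.2%.

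The formula takes the start of counting as independent of the episode. It does not model an open episode supplying the unvaccinated index claim.

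**4. PCV13-CAP odds ratio with no true effect.** Add the carry-over to the CAP risk in each arm.
- Equal carry-over: 1.00.
- Vaccinated arm carries half, low case: 0.99.
- Vaccinated arm carries a quarter, high case: risks 0.04066 and 0.04266, so OR = (0.04066/0.95934) / (0.04266/0.95734) = 0.95.
- Arms swapped: the reciprocals, 1/0.99 = 1.01 to 1/0.95 = 1.05.

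**5. With a true effect.** Assume an unvaccinated CAP risk p₀ of 3%, 5% or 8% and a true risk ratio of 0.90 (true OR 0.89 to 0.90). With carry-over c₀ (unvaccinated) and c₁ (vaccinated), the counted risks are q₀ = p₀ + (1 − p₀)c₀ and q₁ = 0.9p₀ + (1 − 0.9p₀)c₁.

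| c₀ | c₁ | Observed OR over the three p₀ |
|---|---|---|
| 0.1% or 0.5% | equal to c₀ | 0.89 to 0.91 |
| 0.5% | 0.1% | 0.80 to 0.85 |
| 0.1% | 0.5% | 0.94 to 1.03 |

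Example, p₀ = 5%, c₀ = 0.5%, c₁ = 0.1%: q₀ = 0.05475, q₁ = 0.045955, OR = 0.0482 / 0.0579 = 0.83. The 0.5% value (50 per 10,000) is nearly twice the top of the range in step 3, so these rows are a stress test.

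**6. Sampling error.** Treating the roughly 25 million eligible adults as segments at 2:3 with 5% CAP, the unweighted standard error of the log odds ratio is √(1/(25,000,000 × 0.4 × 0.05 × 0.95) + 1/(25,000,000 × 0.6 × 0.05 × 0.95)) = 0.0019. Even the smallest unequal shift in step 4 (0.0057 on the log scale) is about 3 standard errors. This shows only that the confidence interval will not absorb such a bias, not that the bias is large.

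**The case against.** **Exclusion 5 is not described as an incident-CAP rule.** Its stated aim is to equalize the risk that follows recent severe pneumonia, and pairing it with an outpatient-pneumonia covariate is a coherent choice. That stands as an account of the exclusion. It does not make the mediator count only new episodes.

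**Weighting may balance prior outpatient pneumonia.** It may balance how common it was over the year. A yes/no covariate does not balance recency, does not reach days 0-13 after vaccination, and does not stop a repeat code from being counted. The final propensity-score list is also left to the SAP.

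**Mediation details are deferred to the SAP, which is not at hand.** Section 9.7 does say so, but Table 3 already fixes the operational definition. The point concerns a stated rule, not a missing one.

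**A reader might infer that the error manufactures a PCV13 benefit.** The documents do not support that. The arms differ in ways that could make carry-over unequal: the unvaccinated index is itself a claim and counts from day 0, while vaccinated counting starts at day 14. But nothing in the protocol shows which arm carries more, or that PCV13 is given mainly when people are well. The reverse imbalance hides benefit.

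**A reader might also infer that all recent outpatient pneumonia is miscounted, or that the hospital-only analysis is free of the problem.** Neither holds. A further code in the window is needed, and its frequency is unknown. Conversely, someone with outpatient pneumonia just before index who is admitted for it during follow-up passes exclusion 5 and meets the hospital-only definition.

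**Conclusion.** The point holds as a misclassification of the mediator for secondary objective 4. Followed as written, Table 3 scores CAP for a repeat code from an episode that began before index or before day 14. The primary MACE hazard ratio does not use the mediator and is not affected.

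Size and direction are not determined by the documents. Under the assumed rates, 1.1% to 6.2% of counted CAP would be carry-over. The null PCV13-CAP odds ratio would be about 1.00 with equal carry-over, 0.95 to 0.99 if the vaccinated arm carries a half to a quarter as much, and 1.01 to 1.05 if the imbalance is reversed. Equal carry-over leaves that odds ratio almost unchanged but still puts old episodes into the CAP-MACE model. The size of that second effect was not calculated.

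The change is worth making because it is cheap and the planned sensitivity analysis does not correct the main result.

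**What to change.** In the main CAP row of Table 3, add that a code counts only if there is no pneumonia code in any setting in a pre-specified interval before it. The look-back should run across the index date and across days 0-13 of vaccinated segments, and apply identically in both arms. An interval of 90 days is one option. Thirty days, the protocol's existing CAP look-back, is an alternative, though it lets through repeat codes more than 30 days apart. Neither length is dictated by the documents. Every segment has at least six months of prior enrollment, so either is observable.

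Alternatively, for the mediation analysis only, exclude segments with a pneumonia code in any setting in that interval before counting starts. Exclusions 5 and 8 can stay as they are for the primary analysis.

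The cost is one sentence and a few lines of programming on claims already held. The downside is that a true second pneumonia inside the interval is not counted. Because CAP is scored 0 or ≥1, this matters only where the preceding code falls before counting starts.

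A first pneumonia code on the unvaccinated index day is a separate time-zero issue. This look-back does not solve it, and it needs its own rule.
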